### **15. WITHDRAWAL OF SUBJECTS WITHOUT THEIR CONSENT\***

Individual subjects may be withdrawn without their consent if while monitoring the device placement site more than minor skin irritation is noted or if surgeon or other members of the operating room team request device to be removed.

### **16. RISKS TO SUBJECTS\***

There is a minimal risk for increased infection or skin irritation at the device placement site. There are no psychological, social, legal, or economic risks.

**Infection control concerns:** Existing research on laptop disinfection suggests that wiping down the laptop with a Sani-Cloth CHG 2% wipe will meet antimicrobial standards for the hospital setting and will not affect computer functionality or appearance. The laptop will be cleaned with Sani-Cloth CHG 2% wipe before and after each use.

The ViTrack device consists of a white cuff which encircles the wrist and a blue plastic c-clamp that holds white cuff in place on the wrist (see Figures 1 and 2 on page 2). The white cuff is disposable. The blue plastic clamp will be cleaned with Sani-Cloth CHG 2% wipe before and after each use.

**Risk of Confidentiality Breach:** Efforts will be made to limit access to the subject's personal information, including research study information and medical records, to people who have a need to review this information. Dynocardia, the study sponsor, FDA, UMMS Institutional Review Board and other representatives of UMMS may need to review records of individual subjects. As a result, they may see a subject's name, but they are bound by rules of confidentiality not to reveal subject's identity to others or discuss study with others not involved with this research study. Sponsor may only see subject initials and study ID #. All other data will be de-identified for review purposes.

### **17. POTENTIAL DIRECT BENEFITS TO SUBJECTS\***

Subject will not directly benefit from being in this research study.

### **18. VULNERABLE POPULATIONS\***

NA. We will not be enrolling pregnant women, patients younger than 18 years of age or prisoners.

### **19. MULTI-SITE RESEARCH\***

NA

### **20. COMMUNITY-BASED PARTICIPATORY RESEARCH\***

NA

### **21. SHARING OF RESEARCH RESULTS WITH SUBJECTS\***

Subjects will not receive any study results.

### **22. SETTING**

Fact sheet will be reviewed, and signature will be obtained in the pre-anesthesia clinic, hospital bed or the pre-surgical admission unit. The study itself will be performed in the operating room and/or the Intensive Care Unit. Data will be collected continuously by a laptop computer. After surgery, the password protected computer and device will be stored in the Clinical Science Wing of the Department of Anesthesiology and Perioperative Medicine in a locked cabinet in a locked office.

### **23. RESOURCES AVAILABLE**

- Faculty and research personnel from the Department of Anesthesiology and Perioperative Medicine
- Principal investigator, co-investigators, statistician, research assistant, research coordinator and research nurse.

#### Principal Investigator:

This position requires advanced training in Anesthesiology and experience with research design and laboratory methods. The Principal Investigator (PI) Oversee the clinical research protocol, study staff and data analysis. PI is responsible for ensuring that all team members have current CITI training and that Good Clinical Practice is maintained throughout the study. Also ensures all study staff are appropriately trained for their respective roles, including knowledge of formed consent; and apply the ViTrack device.

#### Sub-Investigators:

## **INVESTIGATOR STUDY PLAN - REQUIRED**

This position requires advanced training in Anesthesiology and experience with research design and laboratory methods. Sub-Investigators may be responsible for consenting subjects, data analysis and performing any other study related procedures that fall within their scope of practice only after receiving the appropriate training required to perform the procedures.

### **Statistician:**

This position requires training in statistics. Statisticians may be responsible for data analysis and performing any other study related procedures that fall within their scope of practice only after receiving the appropriate training required to perform the procedures.

### **Research Coordinator/Research Assistants:**

Research coordinators and assistants are specialized research professionals working with and under the direction of the PI. They support, facilitate and coordinate the daily clinical trial activities and play a critical role in the conduct of the study. Other responsibilities include: maintaining records, handling IRB submissions, data management and performing any related procedures that fall within their scope of practice only after receiving the appropriate training required to perform the procedures

### **Research Nurse Coordinator:**

This position requires a registered nurse with Basic Life Support certification (BLS). They are responsible for completing all Joint Commission required annual competencies to practice in the hospital. Research nurse may handle IRB submissions, oversee regulatory requirement, screen and consent subjects and perform any related procedures that fall within their scope of practice only after receiving the appropriate training required to perform the procedures.

A trained and experienced research assistant, research coordinator, research nurse or sub-investigator will perform various tasks required by the study at various time points. A trained and experienced research assistant, research coordinator, research nurse or sub-investigator will enter subject data in to the CRF, and perform regulatory functions required for the study.

### **Time that will be devoted to conduct and complete the research:**

Adequate time has been allocated for enrollment, collection of subject data, history, demographics and data analysis. The PI, research staff and sub-investigators will work the necessary hours to complete the project.

### **Process to ensure that all persons assisting with the research are adequately informed about the protocol:**

All research personnel that are involved in the protocol will be trained at the initiation visit. If they are unable to attend the initiation visit, the PI or a person they feel is appropriately knowledgeable will provide training including: the flow of the research study, procedures required by the protocol, the researcher's duties and functions. A signature log of all that

## **INVESTIGATOR STUDY PLAN - REQUIRED**

trained will be kept in the Regulatory Binder of the study. The binder is kept in a secure location with minimal access to unauthorized personnel (in the clinical research office). The clinical staff caring for the subject will be given information regarding the study.

Prior to commencement of the study, a meeting will be held to review the roles and responsibilities of study personnel. The study will be explained to the surgeons before the study and their assent will be obtained. In addition, other OR personnel will be briefed about the study before the patient arrives in the operating room.

### **24. LOCAL RECRUITMENT METHODS**

Patients will be screened and recruited based on the probability of having an arterial catheter inserted for the surgery. There are more than enough patients who require arterial catheterization in one year to reach our end point.

Patients will be identified prior to the pre-operative appointment and the provider will determine if an arterial catheterization is likely. Every effort will be made to review study and obtain signature on fact sheet at the pre-operative appointment after provider has discussed study and obtained permission from patient for research staff to approach the patient. Otherwise they will be approached in the pre-anesthesia clinic, hospital room, or Surgery Admission Care Unit (SACU) prior to administration of any medications that could alter their ability to review, understand and sign fact sheet. The study will be described to them, fact sheet reviewed, questions or concerns addressed, and signature will be obtained. The patient's clinical provider will obtain permission from the patient for research staff to approach the patient.

Identifiers will not be recorded.

### **25. LOCAL NUMBER OF SUBJECTS**

Thirty (30) patients will be recruited between the University and Memorial Campuses. We are allowing a screening failure of 50% (significant differences in BP between arms; inability to insert arterial catheter).

### **26. CONFIDENTIALITY**

See section 11. Procedures Involved for data to be collected.

All records will be de-identified so each subject is identified by a study ID # and their name will be known only to the researchers. The study ID # will be linked to the subject's MRN via a separate ID log that contains only the MRN and Subject ID. The ID log will be stored separately on a UMMS secure drive. Background information and medical history will be stored on UMMS RedCaps secure network. RedCap is a recommended and preferred data storage site at UMMS. BP and heart rate data will be stored on the study laptop. The subject's name will not be used in any reports or publications of this study. The U.S. Food and Drug Administration (FDA), sponsor and the UMMS Institutional Review Board and/or their representatives may inspect the subject's medical records that pertain to this research study. Sponsor may only see subject initials, study ID #, and de-identified results/data. Data stored on the study laptop will be de-identified as well.

## **INVESTIGATOR STUDY PLAN - REQUIRED**

All persons accessing patient records must adhere to the following guidelines:

- The information in a patient's record cannot be disclosed without the parent/guardian's knowledge and consent; however, there are occasions when there is a legal obligation or duty to disclose information. Requests for patient information from external sources must be directed to the Medical Records Department.
- Medical records must not be left unattended where unauthorized persons might read them. Access to business information, including billing information, is also granted on a need-to-know basis.
- No patient records will be left open on a computer unless actively in use.
- Patient records will be closed as soon as the necessary information has been retrieved.
- Computers with access to patient medical records will be locked unless actively attended

### **Who is responsible for receipt or transmission of the data or specimens locally:**

The research nurses/coordinators and the investigators will be responsible. Transcription of files will take place by the primary sub-investigator, so there will be no additional transmission of files. The only identifier used throughout the transcription process will be the study ID number. These transcripts will be de-identified further (using removal of any subject's name or other PHI) and treated as non-PHI data along with automated logs, etc. They can be shared in the same manner as the other data gathered during the study.

### **How will data be collected and transported:**

Data collected will be collected in hard copy or by electronic medical record. Each subject will be issued a study ID # that will correspond with the information listed on the Data Collection Form. If any paper records need to be transported, they will be placed in an envelope marked confidential and individual transporting records will keep record with them until it can be appropriately locked or transcribed to an electronic format. Electronic data transportation will utilize a UMMS encrypted USB drive/secure network drive.

### **Where and how will data be stored:**

All computerized data will be stored on secured computers or network servers/drives. All paper records will be kept in a locked file cabinet in the Critical Care Research office which is secured with a lock. The electronic data is protected in a database that is password protected and encrypted.

**How long will data be stored and when/how will data be securely destroyed:** The study documents may be retained in the files of the responsible investigator for 5 years. However, these documents will be retained for a longer period if required by the applicable legal requirements. After that period of time the documents may be destroyed, subject to local regulations (shredded or disposed in appropriately labeled and locked "HIPAA bins").

### **Which staff will have access:**

These data will be accessible only by approved research staff, using confidential usernames and passwords. Direct patient identifiers will be removed from study data files as soon as possible in the data processing steps. Statistical analyses will be performed using a limited dataset. All information linking identifiable data to analysis files will be kept separate from analysis files.

## **INVESTIGATOR STUDY PLAN - REQUIRED**

All data will be used only for research purposes only; published data will not contain any individual identifiers, only aggregate-level data will be reported.

Only study personnel included in IRB applications have access to project-specific data. All persons collecting or handling data are trained in human subjects' procedures, confidentiality and privacy protection. All investigators and project staff are required to receive and complete IRB and HIPAA training.

Risks to confidentiality of the data collected throughout the proposed study will be addressed as follows: Assurance and confidentiality of information will be made to all participants. Data will be handled with the same confidentiality accorded to patient's medical records. Specific procedures protecting participant confidentiality will be as follows:

- ID number, as well as full name, medical record number, and dates of service will be placed on electronic study forms or records on which data are collected and/or stored.
- Access to data files will be secured with a password-filing system (that logs entry) and is restricted to authorized staff only.
- Necessary hard-copy records containing study data of any type will be kept in locked files. Master lists linking participant information with ID number will be numbered consecutively and prepared before data collection to ensure accurate accounting. These lists will be kept locked, in duplicate, with access only by the PI and other investigators.
- All reports and publications will preserve the subjects' anonymity.
- Any breach of confidentiality will be subject to a root cause analysis and preventive measures taken as appropriate. We will report any breach of confidentiality as required. A [Certificate of Confidentiality](#) will not be sought.

### **27. PROVISIONS TO PROTECT THE PRIVACY INTERESTS OF SUBJECTS**

Research personnel have extensive experience in conducting clinical trials. This research involves minimal to no risk to the patient. Sufficient time will be allowed for the patient to decide to participate in the study.

We are requesting a HIPAA waiver of authorization. A HIPAA waiver is necessary for screening purposes.

### **28. COMPENSATION FOR RESEARCH-RELATED INJURY**

NA

### **29. ECONOMIC BURDEN TO SUBJECTS**

NA

### **30. CONSENT PROCESS**

All study personnel will have completed required CITI training prior to their addition to the study. Regular upkeep will be done to assure compliance with IRB. Fact sheet and HIPAA authorization review and signatures of the patient or their legally authorized representative (LAR) will occur either at the pre-surgical visit or in the pre-anesthesia clinic, hospital room, or

## **INVESTIGATOR STUDY PLAN - REQUIRED**

surgical admissions care unit prior to their surgery and prior to any medication administration that could affect the ability for subject to understand and sign the fact sheet. All patients will be given the necessary time to review the fact sheet and ask any questions prior to obtaining signature.

### **31. PROCESS TO DOCUMENT CONSENT IN WRITING**

This research presents no more than minimal risk of harm to subjects, therefore we are requesting a waiver of written informed consent. We will instead use a fact sheet. All patient's will be given the necessary time to review the fact sheet and HIPAA authorization form and ask any questions prior to obtaining subject or LAR signature on the fact sheet and HIPAA authorization form.

All study staff will confirm and document that the fact sheet and HIPAA authorization was reviewed with the patient and/or LAR. The patient/LAR will be given a copy of the fact sheet and HIPAA authorization form. All study staff will follow [HRP-802 INVESTIGATOR GUIDANCE: Informed Consent](#).

### **32. DRUGS OR DEVICES**

When the ViTracks are not in clinical use, they will be stored in a locked room of the Clinical Science Wing of the Department of Anesthesiology and Perioperative Medicine. IND exempt due to the device being a class 2 device.

The ViTrack continuous non-invasive BP measurement (cNIBP) device is a non-significant risk device and as outlined in 21CFR812 does not need an IDE application approved by the FDA.

- It is not an implantable device and does not present a potential for serious risk to the health, safety, or welfare of a subject.
- It is not purported or represented to be used for supporting or sustaining human life and does not present a potential for serious risk to the health, safety, or welfare of a subject.
- It is not for use of substantial importance in diagnosing, curing, mitigating, or treating disease, or otherwise preventing impairment of human health and does not present a potential for serious risk to the health, safety, or welfare of a subject.

## Statistical and Data Analysis Plan:

A total of n=30 patients were recruited to optimize the ViTrack technology and compare its performance to radial invasive arterial lines. A total of n=24 patients were used to optimize hardware, device form factor, algorithms, and usability. Then, we used the updated version of the ViTrack device to compare the device performance on 6 patients undergoing vascular surgery in the University of Massachusetts Medical School.

The data was analyzed following the AAMI SP10:2008 standard. Both ViTrack and Invasive arterial pressure data were averaged over a 20-second non-overlapping window, thus providing a paired measurement for comparison every 20 seconds. The average length of the surgery was ~3 hours. After clearing out the segments (both in IAP and ViTrack) affected by motion artifacts, we used the remaining segments for accuracy analysis. Since each dataset might not have a similar number of data points to compare, we weighted the samples to avoid bias to one dataset. A total of 2800 data points across 6 subjects were used for comparison. As per the FDA standard ANSI/AAMI SP10:2008 or the newly adopted ISO 81060-3:2022 standard, the mean error should be <5mmHg or <6mmHg and the standard deviation should be <8mmHg or <10mmHg respectively. We have analyzed ViTrack data on 6 patients and showed the results in **Figure 1** below. ViTrack showed far higher accuracy for both SBP (mean error = 0.19 mmHg [SD = 5.70 mmHg]) and DBP (mean error = 0.90 mmHg [SD = 5.97 mmHg]) measurements when compared to either of the recognized standards [**Fig1**].

**Fig 1: Performance of ViTrack Vs. IAP after motion artifact correction in 6 operating room patients undergoing vascular surgery.**

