### **13. Data Analysis and Management\***

A minimum of 255 data points will be selected by random computer generator from each patient's arterial line and ViTrack recordings. The analysis of 255 time points per patient will be used to compare ViTrack with arterial line measurements. For each sample data point, a "ten beat epoch average" will be calculated, i.e. four beats prior and six beats after (including the sample point itself) will be averaged. Differences in device readings will be calculated as ViTrack minus arterial line values. In addition, Bland Altman plots will be used to determine agreement between the two devices. Our protocol will greatly exceed the AAMI guidelines by examining 255 paired measurements per patient for a minimum total of 5100 time points across 30 patients.

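### The SAP removes motion-affected segments, including ViTrack's own, without a stated rule or count, and averages over 20 seconds instead of ten beats; both steps can lower the reported SDs, by an unknown amount

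*SAP*

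**What the plan says.** Protocol section 13 (Data Analysis and Management): "A minimum of 255 data points will be selected by random computer generator" for each patient. Each point is a ten-beat average and agreement is shown by Bland-Altman plots. No artifact exclusion is stated. Section 10 defines the endpoint as the accuracy of continuous BP measurement.

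The SAP (Statistical and Data Analysis Plan) does something different in two respects.

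- Exclusion: "After clearing out the segments (both in IAP and ViTrack) affected by motion artifacts, we used the remaining segments for accuracy analysis". The text does not define an artifact, name a detection method or threshold, say who judged it or what they could see, or give the number removed by signal or patient.
- Averaging: both signals were "averaged over a 20-second non-overlapping window".

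On quantity it says "The average length of the surgery was ~3 hours" and "A total of 2800 data points across 6 subjects were used for comparison". It reports SDs of 5.70 mmHg (SBP) and 5.97 mmHg (DBP) and compares them with limits: "the standard deviation should be <8mmHg or <10mmHg respectively". It concludes that "ViTrack showed far higher accuracy for both SBP" and DBP than either standard requires. The caption of Figure 1 reads "Performance of ViTrack Vs. IAP after motion artifact correction in 6 operating room patients undergoing vascular surgery"; the figure itself is not shown in the copy reviewed.

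**The concern.** Excluding time when the arterial line is unreadable is defensible, because there is then nothing to compare against. Excluding time because the ViTrack signal is disturbed is different. If the device still gives a value then, that value is part of its performance as a continuous monitor, and dropping it makes the accuracy estimate conditional on the device having a clean signal. Without a written rule applied blind to the paired difference, a reader also cannot rule out that large differences influenced what was called an artifact.

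The averaging change can act in the same direction. A mean over more beats smooths beat-to-beat error more than a ten-beat mean does, by an amount that depends on how strongly successive beat errors are correlated.

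At stake is the SAP's main conclusion. The sentence claiming accuracy well beyond both standards is not itself limited to motion-free, 20-second data, and the SAP does not say that either step departs from the protocol.

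**Working it through.** **Plan's own figures.** The SDs are observed results and cannot be reproduced without the data. What can be checked is how much data they rest on, and how sensitive they are to the two steps.

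**Retained data.** Inputs from the SAP: 2,800 windows, 20 s each, 6 patients.

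2,800 / 6 = 467 windows per patient; 2,800 × 20 / 3,600 / 6 = 2.59 h per patient.

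**Share absent.** Recording time is not stated, so it is assumed: 2.6 h (just above what was retained), 3 h (the SAP's approximate surgery length), 3.5 h (intermediate) and 4 h (the approximate participation time in Protocol section 9).

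Windows available W = 6 × hours × 180. Share absent f = 1 − 2,800 / W.

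**SD the absent windows would need.** With kept SD s (5.70 or 5.97) and limit L, the full-record SD equals L when the absent windows have SD

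X = √[(L² − (1 − f)s²) / f].

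This assumes equal mean error in kept and absent windows. It ignores the SAP's weighting by dataset, because no per-patient counts are given.

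| Assumed recording | W | Absent | f | X for L = 8 (SBP/DBP) | X for L = 10 (SBP/DBP) |
|---|---|---|---|---|---|
| 2.6 h | 2,808 | 8 | 0.3% | 105/100 | 154/150 |
| 3 h | 3,240 | 440 | 14% | 16/16 | 23/23 |
| 3.5 h | 3,780 | 980 | 26% | 12/12 | 17/17 |
| 4 h | 4,320 | 1,520 | 35% | 11/11 | 15/15 |

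Example at 3 h, SBP, L = 8: √[(64 − 0.864 × 32.49) / 0.136] = 16.3 mmHg, which is 2.85 times the kept SD. For DBP it is 15.6 mmHg, 2.62 times.

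At 2.6 h the removal is practically irrelevant. At longer recordings the SD needed falls to about twice the kept SD. These rows are illustrations, not bounds, and windows may be absent for reasons other than motion.

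**Averaging.** At an assumed 75 beats/min, 20 s holds 25 beats, against ten in the protocol. For beat errors with an assumed AR(1) correlation ρ, the variance of a k-beat mean is proportional to

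V(k) = [k + 2 Σ (k − j)ρʲ] / k², summed over j = 1 to k − 1.

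The implied ten-beat SD is s × √[V(10) / V(25)].

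| ρ | Ratio | Ten-beat SD, SBP/DBP |
|---|---|---|
| 0.99 | 1.025 | 5.8/6.1 |
| 0.9 | 1.215 | 6.9/7.3 |
| 0.7 | 1.435 | 8.2/8.6 |

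The documents give no beat-to-beat correlation. Averaging may therefore matter hardly at all, or as much as the removal.

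**The case against.** The strongest reply is that no error in the SDs has been demonstrated. Surgery length is approximate, is not recording length, and may not refer to these 6 patients; if recording lasted about 2.6 h, almost nothing was removed. At 3 h the absent windows would need well over twice the kept SD to reach 8 mmHg and about four times to reach 10. This stands. A reader might infer that about 14% of the data were discarded, or that the device would fail a limit on the full record; the documents support neither.

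The SAP also says it followed AAMI SP10:2008, which might supply an artifact rule, and the unseen figure might carry counts. Neither can be checked here. The SAP text quotes no rule from the standard, so the gap in the text remains.

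The clearing is disclosed in the same paragraph as the conclusion and again in the caption. That is fair, but disclosure without a rule, a count or the signal concerned does not let a reader judge the effect.

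Motion artifact may reflect handling of the limb rather than a fault of the device, and the parenthesis naming both signals could mean that segments were dropped as pairs. Either is possible. The more natural reading is that an artifact in either signal led to removal, and only a written rule would settle it.

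Finally, the caption speaks of correction where the text speaks of clearing. A reader might infer that data were altered. One caption word does not support that, since the text says the remaining segments were used; the wording needs only to be made consistent.

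**Conclusion.** The concern holds as a departure from the protocol that can favour the device, of unknown size. The SAP removes data on the test device's own signal with no criterion, blinding or removed count in its text, and uses a different averaging unit from the one planned. The SDs of 5.70 and 5.97 mmHg therefore describe motion-cleared, 20-second data, and the accuracy statement is supported only to that extent.

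It is tempting to call the removal the main problem and the averaging a minor one. The documents do not allow that ranking: the result depends on recording time and on the SD of the absent windows for one, and on beat-to-beat correlation for the other, and none of these is given. Nor is a breach of 8 or 10 mmHg shown. The calculations rest on assumed recording times, an assumed heart rate, an AR(1) error model, equal mean errors and no weighting. The point should be fixed before the accuracy statement is relied on; confidence is medium because the figure and the standard could not be seen.

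**What to change.** From the stored recordings of the 6 patients, report two results side by side:

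- (a) Exclude only segments where the arterial-line reference is invalid, by a written rule applied without sight of the ViTrack trace or the difference. Keep every ViTrack value, and count the points where the device gives none. The protocol has no artifact rule, so label this one as an addition.
- (b) The present clearing, with its rule written down.

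Give both on 20-second windows and on the protocol's random ten-beat points with Bland-Altman limits. Use more than the floor of 255 points per patient: 6 × 255 = 1,530 falls short of the 1,570 pairs in the protocol's own sample-size statement. Since 1,570 / 6 = 261.7, at least 262 per patient are needed (6 × 262 = 1,572).

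Report recording time, and the number and percent removed, per patient and by signal. Use one term for the clearing step in the text and the caption. If only the motion-cleared 20-second result supports the accuracy statement, limit the statement to motion-free 20-second averages.

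The cost is some re-analysis and rewording, with no new patients. The reported SD will probably be larger. Precision does not improve, because there are still only 6 patients.
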